### 1.1. Overview of Device/Procedure

The study objective is to validate STAGE images and, when applicable, their equivalence to conventional MRI through an assessment by a trained certified neuroradiologist in a clinical setting.

The data collected in this study will be utilized to support an FDA 510(k) submission to gain FDA clearance to market the FDA Class II STAGE system in the United States.

*This study does not involve comparing test subjects vs. control subjects, nor does it involve any treatment and follow-up.*

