### 4.2. Primary Endpoints

4.2.1. Primary Endpoint 1: each STAGE and MRI input or output is graded qualitatively by an experienced individual at the MRI center. Quality grading is performed on a 5-point scale [5=excellent; 4=good; 3=acceptable; 2=poor; 1=unacceptable] on several criteria [blurring/ghosting/ringing; flow artifact; intensity and homogeneity; signal to noise ratio; susceptibility artifacts]. For the questions with a 5-point score, the points will be averaged with scores  $\geq 3$  can be used for clinical diagnosis.

4.2.2. Primary Endpoint 2: contrast appearance will also be graded on a binary basis: passed, failed. All binary questions should have a 'Pass' answer will qualify as "Passed."

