#### **MRI Scan**

Total study time which includes the patient intake and the scans may take up to two hours.

The subject will undergo a brain MRI scan using the STAGE Protocol\* either at 3 Tesla or 1.5 Tesla field strength. The STAGE protocol consists of two flow-compensated spoiled 3D gradient-echo multi-echo scans, run at different specific flip angles.

For 3T\*\* scan parameters are as follows: FOV: 256x192 mm, matrix size: 384x288 or 384x384, slices:  $\geq 64$ , slice thickness: 1.34mm and 2mm, TE= 7.5/12.5/17.5ms, bandwidth per pixel <240Hz, and TR=25ms. Two multi echo scans will be run: with FA = 6° and one with FA = 24°. Data will be collected with In-plane resolutions of 0.67x1.33mm and 0.67x1mm (freq dir x phase dir). Scanner options for partial fourier and elliptical sampling should be turned on if available. The total protocol time will be roughly 5 minutes.

For 1.5T\*\*, the scan parameters are: FOV: 256x192 mm, matrix size: 384x288 or 384x384, slices:  $\geq 48$ , slice thickness 2.7mm and 2mm, TE= 10/20/35ms, bandwidth per pixel <200Hz, and TR = 40ms. Data will be collected with in-plane resolutions of 0.67x1.33mm and 0.67x1mm (freq dir x phase dir). Two multi echo scans will be run: One with with FA of 7° and one with 35°.

Upon collection, the subject's raw DICOM files transferred to the PACS system and then manually sent by the user to the STAGE module for post-processing. (*note: the subject need not be present for this step*) The processed STAGE images will be sent back to the PACS system where they remain within the participant's scan folder and are clearly labeled. They can then be viewed at an integrated workstation. Original and temporary data linked to the patient will be deleted from the module after it is processed.

The generated contrasts are the following:

- Enhanced T1-weighted images (T1We)
- Susceptibility Weighted Images (SWI)
- T1 Maps
- Proton Density Maps
- R2\* Maps
- Susceptibility maps (SWIM)
- Pseudo and modified pseudo SWIM
- True SWI (tSWI)
- Dual inversion recovery images of the CSF, White matter, and Gray matter
- MRA
- Maximum or minimum intensity projections of SWI, tSWI, R2\*

Options for outputting sagittal and coronal reformatted images will be provided for the T1We and T1 maps. Additionally, all images will have an option for skull stripping as well as a 1x1x2 sliding window filter.

\*No contrast administration is required in this protocol.

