\*\* These parameters may vary slightly depending on the limitations of the scanner software version.

For the purposes of validation, additional data will be collected as a gold standard to compare with the STAGE inputs outputs. This includes 3D T1 MP-RAGE and proton density weighted imaging, which are to be collected at recommended parameters, but with similar FOV and matrix size to the images in the STAGE imaging protocol. Scan collection times will range from about 5 – 10 minutes, depending on the field strength.

The MD will be given a survey with questions concerning image quality, whether contrasts based on the tissue properties match the input and outputs, or if anatomical structures appear or not.

No biological specimens will be collected in this study. The study involves MR imaging. STAGE involves an Investigational medical device which is labeled for Investigational Use Only, per FDA IDE labeling requirements/research purposes only.

For children (subjects aged 6-17 years) involved in this study, headphones will be provided to ensure comfort. The subject may need to stay still for a time period up to 40 minutes. A sedative may be prescribed by the subject's primary physician to be taken prior to the scan to mitigate motion during the scan. This study will not involve any intravenous sedation. The subject will be informed that he or she can rest shortly between sequences (each sequence may last 5-10 minutes) if needed, and that the study can be stopped at any time if he or she needs.

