### 8.1. Analysis Samples

The data from up to one hundred twenty (120) subjects will be analyzed. A radiologist will review the quality of the STAGE inputs and outputs as acceptable or not acceptable for clinical review as adjunctive imaging. For each image (STAGE and MRI) input or output, the radiologist will answer survey questions which pertain to the contrast quality and the tissue(s) involved. They will be further compared with output from conventional MR images for quality.

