## 8.3. DATA ANALYSIS AND REPORTING OF RESULTS

### 8.3.1.Analysis of Effectiveness Endpoints

- 8.3.1.1. Primary Endpoint 1: The score of each STAGE and MRI input or output across individuals will be analyzed using a Mann-Whitney tests.
- 8.3.1.2. Primary Endpoint 2: General image quality on a binary basis (passed, failed) will be required to pass in all cases where the input data was found to be clinically useable.

Alpha of  $p < 0.05$  will be considered significant.

## 9. ADVERSE EVENT REPORTING.....

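### The plan names conventional comparators for only two contrasts, but its STAGE-versus-MRI comparison is not limited to matched outputs

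*Combined protocol and SAP*

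**What the plan says.** - **Outputs.** Section 7.2 (MRI Scan), under "The generated contrasts are the following", has 11 lines: T1We, SWI, T1 maps, proton density (PD) maps, R2* maps, SWIM, pseudo and modified pseudo SWIM, tSWI, dual inversion recovery images, MRA, and intensity projections.
- **Comparators.** The same section states that "additional data will be collected as a gold standard to compare with the STAGE inputs outputs", and continues: "This includes 3D T1 MP-RAGE and proton density weighted imaging, which are to be collected at recommended parameters". No other conventional sequence is named as a comparator.
- **Grading.** In section 4.2.1, "each STAGE and MRI input or output is graded qualitatively by an experienced individual at the MRI center". The items include flow artifact, susceptibility artifacts, homogeneity and signal-to-noise ratio. An averaged score of 3 or more counts as usable for diagnosis.
- **Comparison.** Section 4.1.1 sets the quality of STAGE contrasts and maps against conventional MR images. Section 8.1 says of the graded images: "They will be further compared with output from conventional MR images for quality". Section 8.2 powers the study on a paired STAGE-minus-MRI difference of 0.5 (SD 1).
- **Test.** Section 8.3.1.1: "The score of each STAGE and MRI input or output across individuals will be analyzed using a Mann-Whitney tests".
- **Qualifier.** Section 1.1 gives the aim as to "validate STAGE images and, when applicable, their equivalence to conventional MRI". The outputs to which equivalence applies are not listed there or elsewhere.

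**The concern.** A quality comparison is informative when the two images differ in how they were produced and not in what kind of image they are. Several grading items in 4.2.1, notably flow and susceptibility artifact, depend on sequence type. If an SWI, R2*, SWIM or MRA score is set against an MP-RAGE or PD-weighted score, the difference mixes STAGE quality with the ordinary behaviour of two different sequences. It could favour either side for reasons unrelated to STAGE.

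The plan has no table matching outputs to comparators, so the difference on which section 8.2 rests is not tied to any particular output. The pairs could also be chosen after scores are seen. Section 1.1 says the data will support a 510(k) submission, so it matters which outputs a comparative statement covers.

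**Working it through.** **1. Match outputs to comparators (both from section 7.2).**

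| Output line | Named conventional image of the same contrast |
|---|---|
| T1We | MP-RAGE |
| PD map | PD-weighted image (a map against a weighted image) |
| T1 map | arguable: MP-RAGE (a map against a weighted image) |
| SWI | none |
| R2* map | none |
| SWIM | none |
| Pseudo / modified pseudo SWIM | none |
| tSWI | none |
| Dual inversion recovery | none |
| MRA | none |
| Projections of SWI, tSWI, R2* | none |

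Unmatched lines: 11 − 3 = 8 if the T1 map counts as matched, 11 − 2 = 9 if it does not.

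**2. Look for a limiting rule.** Section 1.1 has a qualifier. Sections 4.1.1, 4.2, 4.3, 8.1, 8.2 and 8.3.1.1 do not. None of them lists pairs or says whether scores are pooled over outputs.

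**3. Reproduce the stated power.** Inputs from section 8.2: difference 0.5, SD 1, n = 80, two-sided alpha 0.05, paired t-test. The noncentrality is (0.5/1) × √80 = 4.472 with 79 degrees of freedom and critical value 1.990. Power is 99.3%, so the claim of at least 90% holds as a lower bound; 44 pairs would already give 90%. This power belongs to one score difference, for an output that is not specified.

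**4. Power after restricting to two named pairs.** Without adjustment, two independent tests at 0.05 give a family-wise error of 1 − 0.95² = 9.75%. With Bonferroni, alpha is 0.05/2 = 0.025 each, the critical value is 2.285, and the noncentrality stays at 4.472. Power is 98.5% per comparison, assuming that the 0.5 and SD 1 of section 8.2 apply to each pair.

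For a Wilcoxon signed-rank test I approximate by shrinking n by an assumed relative efficiency. At 0.955, 80 × 0.955 ≈ 76 effective pairs give 98.0%. At 0.864, 80 × 0.864 ≈ 69 give 96.7%. Both are at alpha 0.025. Neither efficiency is in the plan.

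**5. Why the missing rule matters (illustrations only; the plan states neither approach).**
- Separate tests of 11 outputs at 0.05: family-wise error 1 − 0.95¹¹ = 43% if independent. Co-registered outputs from the same scans are correlated, so this is an upper illustration.
- One averaged score, with a true difference of 0.5 on 2 of 11 outputs and 0 on the rest: the mean difference is 0.5 × 2/11 = 0.09, and power at n = 80 is about 13% (SD 1 assumed).

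**The case against.** The other side has several good points.

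- **The comparator list is not worded as exhaustive.** This stands. A reader might infer that only two conventional sequences will be acquired; the text shows only that two are named. The statement that "Scan collection times will range from about 5 – 10 minutes, depending on the field strength" does not settle it, because section 7.2 also allows up to 40 minutes of lying still for children. If other sequences are acquired, the plan still has to name them.
- **Section 1.1 limits equivalence.** In part. It shows that a restricted comparison may have been intended, so it is too strong to say that every output is to be tested against MRI. But the qualifier is undefined and absent from the objectives, endpoints and analysis.
- **The endpoints and success rule need no comparator.** Largely right. The cut-off of 3 and the pass/fail grade are absolute, and section 4.3 requires acceptable quality and expected contrasts, not superiority or equivalence. Outputs can also be checked against the STAGE input scans, although these are not a conventional reference image. The defect is confined to the comparison in 4.1.1, 8.1, 8.2 and 8.3.1.1.
- **Generic items such as blurring or signal-to-noise ratio can be scored on any image.** True, so the outputs lack a contrast-matched comparator, not every possible comparator. The sequence-dependent items remain a problem.
- **Scores might be pooled across contrasts.** A reader might infer this, but no section says so.
- **The count depends on judgement.** If no map is accepted as matched to a weighted image, only T1We is matched and the count is 10. Some lines are derivatives of others, so a line count may overstate the gap.

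**Conclusion.** The point holds as a gap in specification. The plan compares STAGE with conventional MRI in general terms, names comparators for two contrasts, and does not say which outputs the comparison covers. About 8 to 9 of the 11 listed lines have no named contrast-matched comparator, so a STAGE-minus-MRI difference for them could not be read as a difference in STAGE quality alone.

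This rests on counting the listed lines as they stand, on accepting the PD map as matched to the PD-weighted image, and on the view that flow and susceptibility artifact scores vary with sequence type. That last view is imaging reasoning; the documents give no data on it.

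The documents do not support the stronger readings that the whole evaluation lacks a valid reference or that the study is underpowered.

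**What to change.** 1. In 8.3.1.1, add a table that marks each STAGE output either as compared with a named conventional image in the same subject or as assessed for acceptability only. From the sequences now named, the pairs are T1We with MP-RAGE and PD map with PD-weighted image, with a note that the second sets a map against a weighted image.
2. Replace the unpaired Mann-Whitney test for these pairs with a Wilcoxon signed-rank test, in line with the pairing assumed in 8.2.
3. Control multiplicity over the two comparisons, for example Bonferroni at 0.025 each.
4. Evaluate all other outputs only against the 4.2.1 cut-off and the pass/fail criterion, and state in 4.3 that no comparative claim is made for them.
5. If other conventional sequences are in fact acquired, name them in 7.2, add their pairs to the table and extend the multiplicity rule.

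The cost is wording, with no extra scans and no increase in the minimum of 80 subjects. The downside is narrower comparative claims.

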### 7.3. Follow-up Procedures

No follow-up procedures are required for this study. As of 8/26/2020, the protocol parameters were optimized to improve the scan quality. Some subjects may be scanned a second time as a replacement data set for the initial scan. A new informed consent form should be signed. In the situation when a participant cannot be recalled/retained within the study then their original data will not be used towards proving the study endpoints, and a new participant will be recruited.

### 7.4. Patient Management

#### 7.4.1. Treatment Failure

n/a

#### 7.4.2. Loss to Follow-up

n/a

## 8. STATISTICAL CONSIDERATIONS AND ANALYSIS PLAN .....

### 8.1. Analysis Samples

The data from up to one hundred twenty (120) subjects will be analyzed. A radiologist will review the quality of the STAGE inputs and outputs as acceptable or not acceptable for clinical review as adjunctive imaging. For each image (STAGE and MRI) input or output, the radiologist will answer survey questions which pertain to the contrast quality and the tissue(s) involved. They will be further compared with output from conventional MR images for quality.

## 8.2. Sample Size Justification

Up to one hundred twenty (120) subjects (aged 6-80 years) will be enrolled in this study, with an expected data attrition rate of 20% which may be due to poor data quality from motion artifact or withdrawal from the study. Eighty subjects, minimum, will provide at least 90% power (with two-tailed alpha of 0.05) to reject the null hypothesis that STAGE images have lower or equal score to conventional MRI images. This was calculated from a paired t-test which has a slightly higher sensitivity than a Wilcoxon-test. Differences of STAGE-scores and MRI-scores will be paired. For the power calculation I assume a mean difference of STAGE-score – MRI-score of 0.5 points with STD =1.

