### 3.2. Justification and Potential Benefit

*To the individual:* There are no benefits for the research subject.

*To society:* Showing that the STAGE protocol has equal to/or better quality than conventional images would have great impact in the clinical realm. Scan times would therefore be reduced, mitigating patient discomfort within the scanner (especially in frail, aged, neurodegenerative subjects, as well as children). The STAGE protocol also an efficient way to collect this many contrasts, and therefore hospitals and imaging centers can increase their throughput. Standardization would also be achieved between manufacturers and field strengths, which allow for ease in longitudinal assessment, repeat scans. Further, standardized data is optimal as input for Artificial Intelligence algorithms for lesion detection, or to discern any abnormalities based on MR signal.

## 4. STUDY OBJECTIVES AND ENDPOINTS .....

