#### 4.1.1. Secondary Objectives

To evaluate the effectiveness of STAGE output data based on the quality of their image contrasts and maps in comparison with conventional MR images.

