### 4.3. Study Success

The study will be considered successful if STAGE data quality is found to be clinically acceptable and generated contrasts are as expected based on statistical testing.

## 5. CLINICAL STUDY DESIGN .....

This is prospective observational, non-interventional cohort study to evaluate the efficacy of the collection protocol and STAGE system processing algorithm. STAGE system output will be compared to the MRI output from the same patient.

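### Section 1.1 names equivalence to conventional MRI as an objective, but the only hypothesis is superiority and no margin is given, so no planned test can support that comparative claim

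*Combined protocol and SAP*

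**What the plan says.** **The comparative aim.** Section 1.1: "The study objective is to validate STAGE images and, when applicable, their equivalence to conventional MRI", to be judged by a neuroradiologist. Section 4.1.1 makes it a secondary objective to evaluate effectiveness "based on the quality of their image contrasts and maps in comparison with conventional MR images", without direction or margin. Section 7.2 (MRI Scan) adds conventional sequences as the reference: "This includes 3D T1 MP-RAGE and proton density weighted imaging". Section 8.1 says the outputs will also be compared with conventional images for quality.

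**The hypothesis and the test.** Section 8.2 gives a minimum of 80 subjects at least 90% power, at a two-tailed alpha of 0.05, "to reject the null hypothesis that STAGE images have lower or equal score to conventional MRI images". The calculation uses a paired t-test on STAGE minus MRI scores, with an assumed mean difference of 0.5 points and SD 1. Up to 120 subjects are enrolled, with 20% attrition expected. Section 8.3.1.1 analyses the scores with a Mann-Whitney test at 0.05. It states no hypothesis, margin or confidence interval.

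**The absolute criteria.** In section 4.2.1 "the points will be averaged with scores" of 3 or more taken as usable for diagnosis. Sections 4.2.2 and 8.3.1.2 require binary items to pass. Section 8.1 has the radiologist rate images as "acceptable or not acceptable for clinical review as adjunctive imaging". Section 4.3 calls the study successful if STAGE data quality is found "clinically acceptable and generated contrasts are as expected based on statistical testing".

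**The concern.** A superiority null that includes equality cannot be rejected, except by chance, when the two methods are equal. Equality is nevertheless the state that section 1.1 hopes to demonstrate. To show equivalence, or that STAGE is not worse, the plan must say how large a deficit would still be tolerable and test against it. No section does so, and none says whether the claim is one-sided (not worse) or two-sided (equivalent).

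If STAGE matches conventional MRI, the comparison will usually be non-significant and the objective will go unanswered, although the scores needed to answer it will have been collected. A margin chosen after the scores are seen would carry little weight, and section 1.1 says the data are meant to support a 510(k) submission.

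The test named in 8.3.1.1 adds a second difficulty. Mann-Whitney treats STAGE and MRI scores as independent samples, whereas 8.2 pairs them within subject.

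**Working it through.** **Inputs from section 8.2:** n = 80 minimum; 120 × 0.8 = 96 expected after attrition; SD of the paired difference 1; assumed difference +0.5; two-tailed alpha 0.05. **Assumptions added here:** margins M of 0.5, 0.4 and 0.3 points (the documents give none), one image pair, and a true difference of 0 for the non-inferiority and equivalence power.

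**1. The plan's own figure.** Power of the paired t-test is 1 − F(t₀.₉₇₅,ₙ₋₁), where F is the noncentral t distribution with n − 1 degrees of freedom and noncentrality d√n/SD. With d = 0.5 and n = 80, the noncentrality is 0.5 × 8.944 = 4.47 and power is 99.3%. This satisfies the stated minimum of 90%, which 44 subjects would already reach. The arithmetic in 8.2 is sound for superiority.

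**2. The same test when scores match.** With d = 0 the noncentrality is 0 for every n. The chance of a result significantly in favour of STAGE is the upper tail, 0.05/2 = 2.5%, at 80, 96 or any other number. With n = 80 it is 14% at a true advantage of 0.1 and 42% at 0.2.

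**3. What a non-significant result shows.** With n = 80 and an observed SD of 1, the half-width of the 95% confidence interval is 1.990/8.944 = 0.22. An observed difference of 0 gives −0.22 to +0.22. An observed difference of −0.20 gives −0.42 to +0.02, which is also non-significant. Whether either interval supports a claim of not worse depends on a margin that the plan does not state.

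**4. Power once a margin is set.** Non-inferiority at one-sided 0.025 uses the formula in step 1 with noncentrality M√n/SD. At M = 0.3 and n = 80 this is 0.3 × 8.944 = 2.68, giving 75.5%. Equivalence uses two one-sided tests (TOST) at 0.05, that is, the 90% interval must lie within −M to +M.

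| M (assumed) | Non-inferiority, n = 80 | Non-inferiority, n = 96 | TOST 0.05, n = 80 | TOST 0.05, n = 96 |
|---|---|---|---|---|
| 0.5 | 99% | 99.8% | 99% | 99.9% |
| 0.4 | 94% | 97% | 94% | 98% |
| 0.3 | 76% | 83% | 69% | 80% |

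Non-inferiority power of 90% needs 44, 68 or 119 analysable subjects at M = 0.5, 0.4 or 0.3. The smallest margin with 90% non-inferiority power is about 0.37 at 80 subjects and 0.33 at 96.

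**The case against.** The strongest reply is that the study does not depend on this comparison. The primary endpoints and section 4.3 concern acceptability and expected contrasts, and a STAGE that equals conventional MRI can meet all of them. The equivalence phrase in 1.1 is qualified and tied to a neuroradiologist's assessment, so it may mean reader judgement and not a statistical claim. The choice of Mann-Whitney is a separate error that would need correcting under superiority too.

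Much of this stands, and it limits the point to the comparative claim. It does not remove the point. The qualifier in 1.1 can restrict which images are compared, but it supplies no criterion for those that are. Section 4.3 refers to statistical testing without saying which test, so a role for the comparison cannot be ruled out. The pairing error is distinct, but the remedy rewrites the same sentence in 8.3.1.1.

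Three stronger readings are not supported:

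- **Section 3.2 as an objective.** A reader might take "Showing that the STAGE protocol has equal to/or better quality than conventional images" as a second comparative aim. It is conditional text about benefit to society and sets no objective or hypothesis.
- **Non-significance read as equivalence.** A reader might infer that the sponsor will do this. No section says so.
- **A flawed power calculation.** The 0.5 points is an assumed STAGE advantage and not a margin. For superiority the stated power is conservative.

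**Conclusion.** The concern holds for the comparative claim. Followed as written, the plan cannot establish the equivalence named in section 1.1: the 8.2 test favours STAGE 2.5% of the time if scores match, and 8.3.1.1 names an unpaired test with no margin. It would go too far to infer that the study as a whole must fail if scores match, because the average score of at least 3, the binary passes and acceptability as adjunctive imaging are unaffected. This should be fixed before comparative scores are examined.

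The 2.5% needs only the two-tailed 0.05 level and a valid paired test. The other power figures rest on SD 1 from 8.2 and a single image pair; those in the table also assume a true difference of 0 and margins chosen here for illustration. If several image pairs must all meet the rule, power is lower, by an amount that depends on how their differences correlate.

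**What to change.** 1. **Section 8.3.1.1.** Replace Mann-Whitney with a paired analysis of each subject's STAGE minus MRI score (paired t or Wilcoxon signed-rank, with a confidence interval for the mean difference). Apply it to a pre-listed set of STAGE outputs that have a collected conventional counterpart, and state in advance how several pairs are combined.
2. **Choose one of two routes.**
   - **(a) Keep the comparative claim.** In 8.2, name it as non-inferiority or two-sided equivalence, with a clinically justified margin M fixed before comparative scores are examined. Conclude non-inferiority if the lower limit of the two-sided 95% interval is above −M, and then superiority if it is above 0. Conclude equivalence if the interval, at a level named in advance, lies within −M to +M.
   - **(b) Drop it.** Remove the equivalence objective from 1.1 and limit conclusions to the absolute criteria and the superiority test.
3. **Section 4.3.** Say whether the comparison is required for success.
4. **Under (a), restate power** in 8.2 for the chosen claim and margin.

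**Cost.** Both routes use scans and scores already planned. Route (b) needs only wording but gives up the equivalence claim. Route (a) needs agreement on a margin, and stated power is less favourable if that margin is tight. At M = 0.3, 90% non-inferiority power needs about 119 analysable subjects against roughly 96 expected. With 20% attrition that means enrolling 119/0.8 ≈ 149, above the maximum of 120. The sponsor would then have to accept the lower power or revisit enrolment. At M = 0.4 the planned minimum of 80 is enough for one pair.
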